Official Study Title: Investigation of the Effect of Elastic Lower Extremity Orthosis on Gait and Balance Parameters in Children With Spastic Cerebral Palsy: A Randomized Controlled Trial

ClinicalTrials.gov Identifier: NCT07122362

Document Date: April 19, 2025

Study Brief Title: Effect of Elastic Lower Extremity Orthosis on Gait and Balance Parameters in Children with Spastic Cerebral Palsy

Study Period: Start: August 25 2025– End: November 01 2025

1. Study Objective

The primary objective of this study is to determine the effect of an elastic lower extremity orthosis, applied in addition to conventional neurodevelopmental treatment, on gait and balance parameters in children with spastic cerebral palsy presenting with an in-toeing gait pattern.

2. Study Design

Single-blind randomized controlled trial

Biostatistician will be blinded to group allocation

Groups will be assigned using simple randomization

3. Study Population

Inclusion Criteria

Voluntary participation

Diagnosis of spastic cerebral palsy

GMFCS level 1–3

Age 18–84 months

Written and verbal informed consent from parents

Exclusion Criteria

GMFCS level 4–5

Botulinum toxin injection or surgery to lower extremities/pelvis in the past 6 months

Sample Size

Each group: 13 participants

Total: 26 participants

Calculated using G*Power with 95% power and $\alpha = 0.05$

4. Intervention

Neoprene elastic lower extremity orthosis

7 days per week, 6–8 hours per day, 8 weeks

In addition to conventional neurodevelopmental therapy

5. Data Collection and Measurements

Demographics: age, sex, height, weight, CP type, GMFCS level

Gait: Edinburgh Visual Gait Analysis (17 parameters)

Balance: Pediatric Balance Scale (14 items, 0–4 points)

Measurements at baseline and after 8 weeks

Video recordings obtained

No personal identifying information included

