## **Statistical Analysis Plan (SAP)**

Analyses will be performed using IBM SPSS Statistics 26.0

Normality assessment: histograms, probability plots, Shapiro–Wilk test, skewness/kurtosis, coefficient of variation

Descriptive statistics: nominal/ordinal → frequencies and percentages, numerical → median ± percentiles or mean ± SD

Categorical variables: Chi-square (Pearson or Fisher)

Within-group comparisons (pre/post): Paired t-test / Wilcoxon

Between-group comparisons: Student t-test / Mann–Whitney U

Significance level:  $p < 0.05$

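### The between-group test is planned without baseline adjustment, and the SAP does not say whether it uses 8-week scores or change; this gives up precision but is not a validity error.

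*Protocol*

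**What the plan says.** Protocol section 2 (Study Design) states: "Groups will be assigned using simple randomization". No stratification, blocking or minimisation is mentioned. Under Sample Size in section 3 the target is "Each group: 13 participants", 26 in total, at 95% power and a 0.05 level. No effect size, SD, test or sidedness is given.

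Protocol section 5 (Data Collection and Measurements) records GMFCS level among the demographics ("Demographics: age, sex, height, weight, CP type, GMFCS level") and schedules the gait and balance assessments at two visits: "Measurements at baseline and after 8 weeks". Eligible children span "GMFCS level 1–3".

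The SAP has one line on the treatment comparison, "Between-group comparisons: Student t-test / Mann–Whitney U", and one on change over time, "Within-group comparisons (pre/post): Paired t-test / Wilcoxon". No regression model or covariate appears. The second line is the only explicit use of the baseline scores, and it looks at each arm separately, so it is not a treatment comparison.

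**The concern.** With 26 children, precision is scarce, and the baseline value of the same scale is usually the best available predictor of the 8-week value. The trial collects it, but the SAP does not use it as a covariate.

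The SAP also leaves the analysed variable open. Testing 8-week scores and testing change are different analyses. Depending on the pre/post correlation, either can be clearly the more powerful, and they can give different answers in the same data. If the choice is not fixed in advance, it can be made after both results are visible.

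GMFCS level is also recorded but used in neither allocation nor analysis, so a chance difference between arms would go uncorrected. This is the smaller part of the point.

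**Working it through.** **Inputs from the documents.** 13 per arm, 26 in total, 95% power, 0.05 level, simple randomisation, scores at baseline and 8 weeks.

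**Assumptions, because the documents give no figure.** Two-sided test; a single, roughly normal score with equal SD at both visits; pre/post correlation ρ = 0.3, 0.5 or 0.7; true effect either 1.0 SD or the effect implied by the sample size. GMFCS has no effect on outcome until step 5.

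**1. The plan's own figure.** The number 13 per group cannot be reproduced without an effect size, so I solved for the effect it implies. For a two-sided t-test with 24 degrees of freedom, the noncentrality is d × √(13/2) = 2.550d. Power reaches 95.0% at d = 1.474.

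**2. Arm sizes under simple randomisation.** Averaging the power at d = 1.474 over Binomial(26, 0.5) arm sizes gives 94.1%. Unequal arms therefore cost under one point.

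**3. Variance of the treatment difference relative to the 8-week score**
- 8-week score: 1
- change: 2(1 − ρ)
- adjusted for baseline: (1 − ρ²), times an average factor of 1 + 1/22 for estimating the slope, with 23 degrees of freedom

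Since 1 − ρ² = (1 − ρ)(1 + ρ), it never exceeds 2(1 − ρ). It beats the 8-week score once (1 − ρ²)(23/22) < 1, that is, once ρ exceeds √(1/23) = 0.21.

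Example at 13/13, d = 1.0, ρ = 0.5. Unadjusted noncentrality is 2.550, power 68.7%; change is the same, because 2(1 − 0.5) = 1. Adjusted: 0.75 × 23/22 = 0.784, and 2.550/√0.784 = 2.88, power about 79%. Averaging over arm sizes brings these to 66.9% and 77.1%.

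**4. Power averaged over simple randomisation**

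| True effect | ρ | 8-week score | Change | Adjusted for baseline |
|---|---|---|---|---|
| 1.0 SD | 0.3 | 66.9% | 52.7% | 69.0% |
| 1.0 SD | 0.5 | 66.9% | 66.9% | 77.1% |
| 1.0 SD | 0.7 | 66.9% | 87.1% | 90.5% |
| 1.474 SD | 0.3 | 94.1% | 84.7% | 95.0% |
| 1.474 SD | 0.5 | 94.1% | 94.1% | 97.7% |
| 1.474 SD | 0.7 | 94.1% | 99.5% | 99.7% |

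Gain over the better unadjusted test: 2.1, 10.2 and 3.4 points at 1.0 SD; 0.9, 3.6 and 0.2 points at 1.474 SD. If ρ = 0, adjustment lowers power from 66.9% to 64.9% at 1.0 SD and from 94.1% to 93.0% at 1.474 SD.

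Rank version, by simulation at 1.0 SD and ρ = 0.3, 0.5, 0.7: Mann–Whitney U about 64%; a ranked model with baseline and a GMFCS term 64%, 71% and 85%.

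**5. What a GMFCS term adds.** Simulated at 1.0 SD under simple randomisation, with 8 of 26 children at level 3 (assumption) and one term for levels 1–2 versus 3. If GMFCS has no effect, baseline alone gives about 68/77/91% and baseline plus GMFCS about 66/75/90%. If level 3 differs by 1 within-stratum SD, the figures are about 73/82/94% and 75/83/94%. Nearly all the gain comes from baseline.

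**6. Chance GMFCS imbalance.** With 6, 8 or 10 children at level 3 (assumption), the proportions in the two arms differ by 30 points or more with probability 8.8%, 13.1% or 14.7%, over arms of any size. Exact 13/13 arms with a gap of at least 4 of 8 such children are a narrower event: 0.155 × 0.2016 = 3.1%. Given a 6-versus-2 split in 13/13 arms and a GMFCS effect of 0.5, 1 or 1.5 within-stratum SD, equal at both visits, the false-positive rate is about 6%, 8% or 11% on 8-week scores, and about 5% on change scores or with baseline and GMFCS in the model.

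**The case against.** The strongest reply is that simple randomisation with a t-test or Mann–Whitney U is a valid, standard analysis, that every gain above rests on an assumed correlation, and that the SAP may intend change scores, which already use baseline. Much of this stands. At the effect the sample size implies, the plan has little power left to gain. Against a change-score test at ρ = 0.7, adjustment adds 3.4 points at 1.0 SD and 0.2 at 1.474 SD. The figures also describe one continuous score, whereas the Protocol lists 17 gait parameters and 14 balance items and names no primary outcome.

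What does not stand is that the SAP already covers the matter. It does not say that change is analysed. Change is also the weaker choice at low correlation: 52.7% against 66.9% at ρ = 0.3 and 1.0 SD.

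A reader might infer three stronger points, none of which the documents support:
- **That baseline scores are unused between groups.** This is certain only for covariate adjustment, because the test may be on change.
- **That simple randomisation without stratification biases the result.** The 5% error rate holds over all randomisations. The 8% to 11% rates need the 8-week-score reading, a GMFCS effect of 1 to 1.5 SD and a 6-versus-2 split together. The documents say nothing on how strongly GMFCS predicts outcome.
- **That 13 per group contradicts simple randomisation.** Simple randomisation does not guarantee 13/13, but this is a wording matter worth under one point of power.

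**Conclusion.** The point holds as a modest improvement in precision together with a gap in specification. The treatment comparison is planned without covariates, and its variable, 8-week score or change, is not stated. Under the assumptions listed, baseline adjustment matches or beats both unadjusted readings at correlations of 0.3 to 0.7. Its advantage over the better of the two is about 2 to 10 points of power at 1.0 SD and under 4 points at 1.474 SD. Below a correlation of about 0.2 it costs a little against the 8-week score. Confidence is high on what the documents say and medium on the size, which depends on a correlation and an effect that they do not give. Nothing here makes the planned analysis invalid.

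**What to change.** Before the biostatistician is unblinded, add to the SAP that each between-group comparison is a linear model of the 8-week score on arm and the baseline value of the same score. Where Mann–Whitney U was planned, use the same model with both scores ranked. This takes one or two sentences and no extra children or measurements, and it removes the ambiguity between 8-week score and change. The cost is one degree of freedom: if baseline is unrelated to outcome, about 1 point of power at 1.474 SD and about 2 points at 1.0 SD.

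Optional: add one GMFCS term (levels 1–2 versus 3). Under simple randomisation it costs about 1 to 2 points if GMFCS is not prognostic, gains at most about 2 at these correlations if its effect is 1 SD, and protects against a chance GMFCS imbalance. If randomisation has not started, a concealed 1:1 list stratified by GMFCS with random permuted blocks makes that term nearly free (about 0.1 point when strata are balanced). Blocks are slightly predictable if their sizes become known, and arms may end slightly off 13/13. If randomisation has started, state the method actually used. Either way, call 13 per group a target unless a fixed list is meant.

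### Simple randomization does not deliver the fixed 13 children per group (13:13 arises only 15.5% of the time), and the protocol does not say how equal groups would be reached

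*Protocol*

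**What the plan says.** Protocol Section 2 (Study Design) gives the allocation method in one line: "Groups will be assigned using simple randomization". Section 3 (Sample Size) gives "Each group: 13 participants" and "Total: 26 participants", obtained from G*Power at 95% power and alpha 0.05.

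Neither document mentions an allocation ratio, blocks, a list, a cap, how the sequence is generated, or how assignments are concealed. The SAP is silent on randomization. On blinding, Section 2 says only "Biostatistician will be blinded to group allocation". For the comparison between groups the SAP lists "Between-group comparisons: Student t-test / Mann–Whitney U" and no covariate-adjusted analysis.

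**The concern.** Simple randomization assigns each child independently, so group sizes are random. A fixed 13 in each group is a feature of restricted allocation. Read literally, the two statements describe different procedures, and nothing in the documents reconciles them.

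What is at stake depends on what the site actually does. If it lets the split fall where it may, the groups will usually not be 13:13 and some power is lost. If it tosses for each child in turn and sends everyone to the other group once one reaches 13, the end of the sequence is known before those children are enrolled. Staff who know the running totals could then influence who enters next. Eligibility spans GMFCS levels 1–3 and ages 18–84 months, so such a choice could shift the groups, and the unadjusted tests in the SAP would not correct for it.

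**Working it through.** **Inputs.** Total 26, 13 per group, power 95% and alpha 0.05 come from Protocol Section 3. The test (Student t) comes from the SAP. Three assumptions are needed because the documents are silent: an assignment probability of 0.5 (inferred from the equal groups), a two-sided test, and an effect size.

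**The plan's own figure.** No effect size, SD or sidedness is given, so 13 per group cannot be reproduced. Working backwards with the noncentral t distribution, 13 per group has 95% power at a standardized difference d = 1.47 two-sided (1.33 one-sided). Only the power results below depend on this.

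**Distribution of the split.** The number in one group is Binomial(26, 0.5).

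- P(13:13) = C(26,13)/2^26 = 10,400,600/67,108,864 = 0.155, so 13:13 is missed 84.5% of the time.
- P(10:16 or worse) = 1 − P(11:15 or closer) = 1 − 0.673 = 0.327.
- P(8:18 or worse) = 1 − P(9:17 or closer) = 1 − 0.924 = 0.076.

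**Power if the split is left to chance.** The noncentrality is d × √(n1·n2/(n1+n2)) on 24 degrees of freedom, with d = 1.474, two-sided alpha 0.05.

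| Split | √(n1·n2/26) | Noncentrality | Power |
|---|---|---|---|
| 13:13 | 2.550 | 3.76 | 95.0% |
| 10:16 | 2.481 | 3.66 | 93.9% |
| 8:18 | 2.353 | 3.47 | 91.4% |

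Weighting the power at each split by its binomial probability gives an average of 94.1%. The one-sided version, with d = 1.33, averages 94.2%.

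**Forced assignments if sequential tossing is capped at 13.** One group first reaches 13 at child m with probability 2·C(m−1,12)/2^m, for m = 13 to 25. The remaining 26 − m assignments are then determined.

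- The mean number forced is 4.03.
- At least 1 is always forced; 4 or more are forced in 52.3% of sequences, and 6 or more in 26.3%.

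**Forced assignments under restricted schemes.** A random list of k and k has an expected determined tail of 2k/(k+1).

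- One list of 13 and 13: 2 × 13/14 = 1.9.
- Permuted blocks of 4, 4, 6, 6 and 6 (total 26), if the block sizes became known: 2 × (4/3) + 3 × (6/4) = 2.67 + 4.50 = about 7.2. This is more than the capped toss, so blocks help only if their sizes stay hidden.
- A one-time draw of 13 from 26 children already enrolled: none.

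**The case against.** The strongest reply is that 'simple' is loose wording and nothing improper is planned. All 26 children could be enrolled first and 13 drawn at once, which gives 13:13 with no predictable tail. The timetable allows it: "Start: August 25 2025– End: November 01 2025" is 68 days, and 8 weeks of treatment takes 56, leaving about 12 days to start everyone. It can also be said that 13 per group is a planning target, and that unequal groups from true simple randomization do not bias the t-test or Mann–Whitney comparison and barely reduce power.

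Most of this stands. A reader might infer that late assignments in this trial will be predictable and the comparison therefore biased. The documents do not support that. It requires one-at-a-time allocation, a cap at 13, staff who know the running totals, and staff who can choose whom to enrol next, and none of these is stated. That only the biostatistician is named as blinded makes knowledge of the totals plausible, since a worn orthosis is visible, but it does not establish the rest. Nor is every run either unequal or forced: 13:13 occurs by chance in 15.5%.

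What the reply does not remove is the mismatch. Drawing 13 of 26 at once is restricted allocation, not simple randomization, and the protocol does not describe it.

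**Conclusion.** The allocation rule as written does not deliver the group sizes as written: it does so in 15.5% of trials, and gives 10:16 or worse in 32.7%. This rests only on 26 children and a 1:1 probability, not on the unstated effect size.

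If no cap is used, the consequence is small: average power of about 94.1% instead of 95%, under the back-solved d = 1.47 and a two-sided t-test, and no bias. A reading that the trial would be seriously underpowered for this reason is not supported. If a sequential cap is used, about 4 of 26 assignments on average would be known in advance, with no described concealment to prevent selection. The documents leave open which case applies. The point should be corrected before enrolment, because it concerns the step that protects the between-group comparison and the correction is cheap. It is not a fatal flaw.

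**What to change.** In Protocol Section 2, replace simple randomization with a restricted 1:1 allocation that ends at 13:13, in one of two forms:

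- one computer-generated random list of 13 and 13; or
- if all children are enrolled and assessed at baseline first, a single random draw of 13 from the 26.

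State that the list is prepared and held by existing staff who do not enrol children, and that each assignment is released only after enrolment and baseline assessment. Permuted blocks are acceptable only if block sizes vary and are hidden from enrolling staff.

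If simple randomization is kept, reword Section 3 as 26 in total with 13 per group expected, impose no cap, and restate power as about 94% averaged over splits under the same assumed effect.

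The cost is a few sentences and a different list-generation step, with no extra children, visits or staff. The small downside of a single list is that about 1.9 assignments at its end are still determined on average; the one-time draw avoids this but requires everyone to be enrolled before anyone starts.

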## **Statistical Analysis Plan (SAP)**

Analyses will be performed using IBM SPSS Statistics 26.0

Normality assessment: histograms, probability plots, Shapiro–Wilk test, skewness/kurtosis, coefficient of variation

Descriptive statistics: nominal/ordinal → frequencies and percentages, numerical → median ± percentiles or mean ± SD

Categorical variables: Chi-square (Pearson or Fisher)

Within-group comparisons (pre/post): Paired t-test / Wilcoxon

Between-group comparisons: Student t-test / Mann–Whitney U

Significance level:  $p < 0.05$

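### The SAP tests pre/post change within each arm beside the between-arm comparison and does not say that only the between-arm comparison can support a conclusion about the orthosis

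*SAP*

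**What the plan says.** Section 1 of the protocol (Study Objective) sets out to determine the effect of the orthosis "applied in addition to conventional neurodevelopmental treatment, on gait and balance parameters". Section 2 calls the study a "Single-blind randomized controlled trial" and states "Groups will be assigned using simple randomization". Section 3 plans 13 children per group, 26 in all, and section 5 schedules measurements at baseline and at 8 weeks.

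The SAP gives one line to "Within-group comparisons (pre/post): Paired t-test / Wilcoxon" and the next to "Between-group comparisons: Student t-test / Mann–Whitney U". One significance level, p < 0.05, covers everything. Descriptive statistics have a separate line, so the within-group line is a plan for hypothesis tests and not for summaries.

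Neither document names a primary outcome, a primary analysis or a deciding test. The SAP also does not say whether the between-group test is applied to 8-week scores or to change from baseline.

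**The concern.** The objective concerns an added effect, so it is a contrast between randomised arms. A paired test in one arm asks a different question: did these children change over 8 weeks? Growth, background therapy, practice with the test or the expectations of unblinded raters can all produce change. The children are 18 to 84 months old, and the only blinding stated is "Biostatistician will be blinded to group allocation". A within-arm p-value cannot separate these sources from the orthosis.

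The familiar misreading is that an effect is shown when the orthosis arm changed significantly and the control arm did not. With small arms, two samples with the same true change can easily fall on opposite sides of 0.05. If the plan does not rule this reading out in advance, the choice of which p-value to rely on can be made after the results are known.

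**Working it through.** **The plan's own figure.** Section 3 of the protocol gives 13 per group for 95% power at α = 0.05. It states no effect size, SD, test or sidedness, so the figure cannot be reproduced, only back-solved.

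- Two-sided two-sample test, normal approximation: d = (1.960 + 1.645) × √(2/13) = 1.41. The noncentral t gives 1.47.
- One-sided: 1.29 and 1.33 respectively.
- Paired test with n = 13, two-sided: standardised change 1.09.

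The documents do not say which of these was intended. For smaller true effects, two-sided between-arm power at 13 per arm is 0.23 at d = 0.5, 0.50 at d = 0.8 and 0.69 at d = 1.0. A non-significant between-arm result beside a significant within-arm result is therefore a realistic outcome.

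**Inputs for the illustration.** From the documents: n = 13 per arm and α = 0.05. Assumed: two-sided tests, normal change scores, and the same true standardised change δ (mean change divided by SD of change) in both arms, so that the orthosis adds nothing. The documents give no value for δ, so a range is shown.

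**Formulas.** The chance p that one arm shows significant improvement is the upper-tail probability, beyond the 0.975 point of t with 12 degrees of freedom, of a noncentral t with 12 degrees of freedom and noncentrality δ√13. The arms are independent, so

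P(orthosis arm significant, control arm not) = p(1 − p).

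This cannot exceed 0.25, the value at p = 0.5. Example at δ = 0.5: noncentrality 0.5 × 3.606 = 1.80, p = 0.382, and 0.382 × 0.618 = 0.236.

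The last column comes from 100,000 simulated trials per row. It adds the condition that the between-arm t-test on change is not significant.

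| Shared change δ (SD) | p | Orthosis arm only, p(1 − p) | Orthosis arm only, and between-arm test not significant |
|---|---|---|---|
| 0 | 0.025 | 2% | 2% |
| 0.2 | 0.098 | 9% | 7% |
| 0.3 | 0.168 | 14% | 12% |
| 0.4 | 0.264 | 19% | 17% |
| 0.5 | 0.382 | 24% | 22% |
| 0.6 | 0.512 | 25% | 23% |
| 0.8 | 0.754 | 19% | 17% |
| 1.0 | 0.911 | 8% | 7% |
| 1.09 | 0.950 | 5% | 4% |

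In the same simulations the between-arm test was significant in either direction in 4.9% to 5.0% of trials at every δ, which is about 2.5% in favour of the orthosis. The shared change does not affect it.

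**The case against.** The strongest reply is that the valid test is already in the plan. The study is randomised, the between-group comparison is listed, and no sentence says that a within-group result will be used to claim an effect. Within-group summaries are routine. On this view the SAP lacks only a clarifying sentence, and the rates above belong to a decision rule that it does not contain.

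Much of this stands, and it rules out several stronger readings.

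- A reader might infer that the plan bypasses randomisation. It does not, because the randomised comparison is planned. What is missing is its precedence.
- A reader might take the table as the trial's type I error rate. It is not. The rates apply only if the orthosis-only pattern is read as an effect.
- A reader might count every trial in which exactly one arm is significant, which gives 37% to 50% for shared changes of 0.4 to 0.8 SD. Half of those are control-only results, which nobody would report as a benefit of the orthosis.
- A reader might treat improvement in both arms as given. The protocol describes only the orthosis arm, as treatment "In addition to conventional neurodevelopmental therapy". That controls receive the same therapy alone is an inference, and that both arms improve is plausible but has no figure behind it.

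The reply does not close the gap. The within-group tests are planned as tests, at the same threshold, and they cannot answer the stated question. A SAP exists to settle such choices before the data are seen.

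**Conclusion.** The point holds as a defect in what the plan permits, not in what it says will be done. The SAP leaves open an efficacy claim from a within-arm p-value when the randomised arms do not differ.

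Under the stated assumptions, with identical arms, the orthosis-only pattern occurs in about 2% to 25% of trials, depending on the shared change, against 2.5% for a valid between-arm test. With no shared change there is no inflation. It peaks near 0.6 SD and has fallen to 5% by 1.09 SD. Simple randomisation may not give exactly 13 per arm, which would shift the figures somewhat. Multiplicity across gait and balance outcomes is a separate matter and is not counted here.

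The plan should be changed before analysis. The trial's design and data collection are not affected.

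**What to change.** Amend both SAP lines. Changing only the within-group line to bring in an adjusted comparison would leave two conflicting between-group analyses.

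1. Within-group line: *Pre/post change within each arm is reported descriptively (mean change with SD, or median with quartiles) without a p-value.*
2. Between-group line: *The effect of the orthosis is judged only from the between-group comparison of the 8-week score adjusted for the baseline score (ANCOVA), reported as a difference with its 95% CI; if model assumptions clearly fail, a rank-based comparison (rank ANCOVA, or Mann–Whitney U on change) is used.*

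The second line also settles whether 8-week scores or change are compared, and it uses a baseline score that is already collected. It keeps a rank-based fallback, which matters because the balance scale is a bounded sum (14 items × 4 points = 56) and only 26 children are planned.

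The cost is small. No new data or participants are needed. The within-arm p-values are no longer available to quote, and one degree of freedom goes to the baseline covariate (26 − 2 = 24 becomes 26 − 3 = 23).

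### The between-group test for gait and balance names no variable to compare and leaves out the baseline score that the trial collects

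*SAP*

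**What the plan says.** Section 5 of the protocol schedules the gait and balance assessments twice: "Measurements at baseline and after 8 weeks". Gait is scored with the Edinburgh Visual Gait Analysis (17 parameters). Balance is scored with the Pediatric Balance Scale, whose 14 items of 0 to 4 points give a range of 0 to 56.

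The SAP's between-group specification is one line: "Between-group comparisons: Student t-test / Mann–Whitney U". It names no variable to be compared and no covariate, and the SAP contains no ANCOVA, regression or mixed model. The only stated test that uses the baseline score is the line before it: "Within-group comparisons (pre/post): Paired t-test / Wilcoxon". Both lines fall under the same 0.05 significance level.

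Section 2 of the protocol says "Groups will be assigned using simple randomization", with no stratification mentioned. Section 3 gives "Each group: 13 participants".

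**The concern.** There are two gaps, and one change closes both.

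First, two analysts who follow the SAP could test different things, the 8-week score or the change from baseline, and report different p-values. Which of the two is more precise depends on the correlation r between baseline and 8-week scores. Below r=0.5 the 8-week score is better; above it, the change score is. Neither document gives r.

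Second, a trial of 26 children has little precision to spare, and simple randomization does nothing to balance the starting scores. If the arms differ by chance at baseline, a comparison of 8-week scores ignores the difference. A change score over-corrects for it whenever r is below 1. ANCOVA removes the part that baseline predicts and does not require r to be known in advance.

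A smaller point is that the SAP does not say whether the within-group or the between-group result decides the conclusion.

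**Working it through.** **The plan's own figure.** The protocol gives 13 per group at 95% power and alpha 0.05, without effect size, SD, endpoint, test or sidedness, so it cannot be reproduced. Solving backwards for a two-sided two-sample t-test with 13 per arm gives a standardized difference d of 1.47 (1.33 if one-sided). This is an inference about the design, not a stated value.

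**Inputs.** From the documents: 13 per arm and alpha 0.05, taken as two-sided. Assumed: r, the effect d in SDs of the 8-week score, equal SDs at both times, and exactly 13 per arm.

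**Power.** Relative to the 8-week score, the variance factors V are:

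- 8-week score: 1, on 24 df
- change score: 2(1−r), on 24 df
- ANCOVA: (1−r²)(1+1/22), on 23 df; the second factor is the small-sample cost of estimating the slope, with 22 = 26−4

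Power comes from the noncentral t with noncentrality d√(13/2)/√V. At d=0.8 the numerator is 0.8×√6.5 = 2.040.

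| r | V: change, ANCOVA | Noncentrality: 8-week / change / ANCOVA | Power: 8-week / change / ANCOVA |
|---|---|---|---|
| 0.3 | 1.40, 0.951 | 2.040 / 1.724 / 2.091 | 50 / 38 / 52% |
| 0.5 | 1.00, 0.784 | 2.040 / 2.040 / 2.303 | 50 / 50 / 60% |
| 0.8 | 0.40, 0.376 | 2.040 / 3.225 / 3.325 | 50 / 87 / 89% |

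Against the less suitable unadjusted test, ANCOVA gains 14 points (52−38), 10 points (60−50) and 39 points (89−50).

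Against the better unadjusted test, the gain is largest at r=0.5:

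| d | 0.3 | 0.5 | 0.8 | 1.0 | 1.2 | 1.47 |
|---|---|---|---|---|---|---|
| Largest gain, points | 1.8 | 5.0 | 9.8 | 10.1 | 7.6 | 3.3 |

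At d=0.8 this gain reaches 5 points only for r of about 0.40 to 0.69. ANCOVA loses to the 8-week test below r of about 0.22, by at most 2.1 points (d=1.0, r=0). Above r of about 0.9 it can lose to the change score, by at most 1 point.

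**Precision without an assumed effect.** The mean 95% CI half-width in score SDs (8-week / change / ANCOVA, 200,000 simulated normal trials) is 0.80/0.95/0.78 at r=0.3, 0.80/0.80/0.71 at r=0.5 and 0.80/0.51/0.49 at r=0.8.

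**Chance imbalance.** The standard error of the baseline difference is √(2/13) = 0.392 SD. A gap above 0.5 SD therefore has probability 2×[1−Φ(0.5/0.392)] = 0.202. With no treatment effect, a baseline gap g produces an expected difference of r·g in 8-week scores, (r−1)·g in change scores and zero after ANCOVA. In that fifth of trials the simulated false-positive rates (8-week / change / ANCOVA) are 7/13/5% at r=0.3, 11/11/5% at r=0.5 and 19/7/5% at r=0.8. Over all trials every method returns to 4.9–5.1%.

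**Bounded score.** To mimic the balance scale, scores were generated as 44+12z, rounded and clipped to 0–56, which puts about 17% at the ceiling. The mean and SD are assumptions. With a latent effect of 0.8, power over 60,000 trials was:

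| Latent r | Mann–Whitney, 8-week | Mann–Whitney, change | ANCOVA | Quade |
|---|---|---|---|---|
| 0.3 | 44% | 27% | 47% | 47% |
| 0.5 | 45% | 35% | 53% | 54% |
| 0.8 | 45% | 65% | 81% | 79% |

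Type I error for ANCOVA and Quade was 5.0–5.2%.

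**Conditional points.** If both unadjusted t-tests were run and either accepted, type I error would be 8.8, 9.2 and 9.4% at r=0.3, 0.5 and 0.8. If both arms improved equally, a result significant in the orthosis arm but not in the control arm would occur in at most 25% of trials, at a mean change of 0.6 SD of the change score. The SAP plans neither practice.

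**The case against.** The planned tests are valid, and the gain from a covariate depends on values of r and d that the documents do not give. If the trial really was sized for d of about 1.47, power for 8-week / change / ANCOVA is 95/86/96% at r=0.3 and 95/95/98% at r=0.5. At r=0.7 it is 95% for the 8-week score and above 99% for the other two, a gain of only 0.2 points over the change score. The 39-point figure arises only if 8-week scores are compared when r is 0.8; simply naming the change score there would recover nearly all of it (87% against 89%). The bounded-score table also compares ANCOVA only with Mann–Whitney. In a rerun of 20,000 trials, Student's t on change reached 30/38/70%, and normality of the change scores was rejected so seldom (about 4–7% of trials) that t would usually be chosen.

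Most of this stands as a limit on size. The gain over a well-chosen unadjusted test is modest, and the advantage over change scores in the bounded model at r=0.8 is about 10 points, not 16. The conditional error rates and the two conditional points do not show that the planned test is invalid. The objection does not supply the missing variable or tell the sponsor which unadjusted test is the better one. The 1.47 is itself inferred, and the true effect may be smaller.

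**Conclusion.** The point holds. As written, the between-group analysis cannot be reproduced, because the compared variable is not named, and it does not adjust for a baseline score that the trial already collects. This is a loss of efficiency and clarity, not a bias.

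The size rests on assumed r and d. ANCOVA gains up to about 10 power points over the better unadjusted test (effects of 0.8 to 1.0 SD, r=0.5) and about 3 points at 1.47 SD. The larger gains, 14 to 39 points at 0.8 SD with r of 0.3 or 0.8, apply only if the less suitable variable is chosen. The plan should be corrected, but the trial would remain valid without the change.

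**What to change.** For the gait and balance scores, replace the Student t / Mann–Whitney line with:

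> For each gait and balance score, the between-group analysis is a linear model (ANCOVA) of the 8-week score on group and the baseline score of the same measure, reporting the adjusted difference with its 95% CI. Quade's rank ANCOVA (groups compared on residuals from the pooled regression of ranked 8-week score on ranked baseline) is reported as a sensitivity analysis. Within-group pre/post results are descriptive; the conclusion on the orthosis rests on the between-group difference.

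Two details go with it. The SAP should say which gait score is meant, a total or the 17 parameters, so that the sentence does not silently become 17 models. Reporting Quade's analysis in every case avoids a normality trigger that depends on the data.

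The cost is a change of SAP wording and one degree of freedom, worth at most about 2 points of power if r is below about 0.22. No new data are needed and the model is standard.
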